5.1.3 Previous and Concomitant Treatment (Medication and NonMedication Therapy)

Subjects will not be allowed to take immunizations, blood product, immunosuppressants including systemic steroids (topical steroids will be allowed) from first study vaccine administration until 30 days postimmunization. Acetaminophen and nonsteroidal anti-inflammatory drugs (NSAIDs) are allowed during the study, but not within 24 hours prior to immunization and collection of serum samples for immunogenicity. Subjects who are taking concomitant medications (3 months prior to study enrollment) to treat pre-existing conditions (e.g., hypertension) must remain on stable doses of these medications throughout the study. The doses of all concomitant medications should remain stable throughout the study, but may be changed for medical reasons as determined by the clinical investigator.

If during the study, a subject's health condition necessitates the use of any medication from those listed above, the investigator and medical monitor or designee(s), will discuss the case and determine if the subject should be withdrawn from the study. The excluded concomitant medication will be recorded as a protocol deviation. All concomitant medication including prescription and nonprescription, vitamins and natural and herbal remedies (e.g., St. John's Wort) will be documented.

Use of systemically absorbed antibiotics during the 30-day period prior to collection of the immunogenicity samples should be restricted unless clinically warranted (e.g., avoid prophylaxis) to avoid interference with the immunoassay. If a subject has been treated with any systemically absorbed antibiotics between day 1 and day 30, the day 30 follow-up visit should take place at least 7 days after the last dose of the antibiotics.

Subjects may receive other routine immunization at the 30-day follow-up visit after the completion of all study procedures at each site's discretion; however, routine vaccines should not be given in less than 30 days after study immunization.

A list of excluded concomitant medications is provided in [Appendix 12.4 List of Excluded Concomitant Medications].

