of age and 75 to 85 years of age) to ensure there is a balanced number of subjects immunized with ASP3772 or PCV13 with immunogenicity data across the elderly population.

Safety and tolerability assessments including AEs will continue through 30 days postimmunization. Safety assessments for SAEs and MAAEs including PIMMCs and NOCDs will continue through day 180 postimmunization. Data will be collected in an observer-blinded manner (vaccine recipients and the site staff who is responsible for evaluation of any study endpoint will be unaware of which vaccine the subject received).

Serum samples to measure IgG and OPA will be collected prior to study immunization on day 1 and postimmunization on day 30.

Primary immunogenicity evaluation for dose finding is 30 days following the initial immunization.

Stage 2 Group 3:

A separate group of elderly subjects previously immunized with PCV13 will be enrolled and receive the recommended booster immunization with PPSV23 only (n = 99). Prior immunization (PCV13) should have taken place no less than 10 months and no more than 2 years prior to study vaccine administration. Immunogenicity to the 11 non-PCV13 serotypes contained in PPSV23 will be evaluated.

Safety assessments will continue through 30 days postimmunization.

Serum samples to measure IgG and OPA levels will be collected prior to study immunization on day 1 and postimmunization on day 30.

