5 IMMUNIZATIONS AND EVALUATION

5.1 Dosing and Administration of Study Vaccine and Other Medications

5.1.1 Dose/Dose Regimen and Administration Period

Stage 1:

Adults 18 to 64 years of age - PCV13 Naïve Subjects (Group 1):

Subjects randomized to ASP3772 will receive a single immunization of ASP3772 as a 0.5 mL intramuscular injection on day 1 at 1 of 3 dose levels: 1, 2 or 5 µg of ASP3772 for Cohorts 1, 2 and 3, respectively. The subjects randomized to PCV13 will receive a single injection of the standard dose of PCV13 on day 1. Follow-up study visits will be conducted at 7 and 30 days postimmunization. The final study visit at day 180 may be conducted via telephone call.

02 Dec 2019 Astellas Page 52 of 111

Stage 2:

Elderly 65 to 85 years of age - PCV13 Naïve Subjects (Group 2):

Subjects randomized to ASP3772 will receive a single immunization of ASP3772 administered as a 0.5 mL intramuscular injection on day 1, at 1 of 3 dose levels: 1, 2 or 5 μg of ASP3772 for Cohorts 4, 5 and 6, respectively. The subjects randomized to PCV13 will receive a single 0.5 mL intramuscular injection of the standard dose of PCV13. Follow-up study visits will be conducted at 7 and 30 days postimmunization. The final study visit at day 180 may be conducted via telephone call.

Elderly 65 to 85 years of age - Previous PCV13 Exposed Subjects (Group 3):

A third group of nonrandomized subjects previously vaccinated with PCV13 will be enrolled and receive a booster immunization (single 0.5 mL intramuscular injection) with PPSV23 on day 1. A follow-up visit will be conducted at 30 days postimmunization and this visit will also serve as the final study visit.

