5.1.5 Criteria for Continuation of Immunization

Formal Stopping Rules for Individual Subjects:

Individual subjects will be discontinued from the study if:

- Subject is lost-to-follow-up despite reasonable efforts by the investigator to locate the subject.
- Subject voluntarily withdraws from the study at any time for any reason.

Formal Stopping Rules for Cohorts:

No additional subjects will be randomized or dosed in the study until the events below occurring in a subject who received ASP3772 are reviewed by the DEC and it is acceptable to resume cohort immunization.

- Unexplained death of a subject.
- Serious acute hypersensitivity reaction in a subject.
- One of the sentinel subjects experiences an AE of severe intensity related to ASP3772, when sentinel subjects are required.
- An SAE of the same character occurs in at least 2 subjects or 1 subject experiences a vaccine-related SAE.
- Grade 3 or higher lab abnormality considered related to the immunization occurs in 2 or more subjects [FDA Guidance for Industry, 2007].
- The same type of reactogenicity event assessed as Grade 3 or higher occurs in 2 or more subjects, or 1 of the sentinel subjects experiences a reactogenicity event assessed as Grade 3 or higher, using the FDA toxicity grading scale for preventative vaccines [FDA Guidance for Industry, 2007].
- An imbalance of unsolicited AEs between ASP3772 and PCV13 is observed.

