5.5.5 Reporting of Serious Adverse Events (SAEs)

The collection of AEs will continue until 30 days after study vaccine administration in all groups. The expedited reporting of SAEs will start following receipt of the ICF and will continue until 180 days after study vaccine administration in Groups 1 and 2 and until 30 days after study vaccine administration in Group 3, or until the subject is determined to be a screen failure or withdraws from the study.

In the case of an SAE, the investigator must contact the sponsor by fax or email immediately (within 24 hours of awareness).

The investigator must complete and submit an SAE worksheet containing all information that is required by local and/or regional regulations to the sponsor by email or fax immediately (within 24 hours of awareness).

The SAE worksheet must be signed by a medically qualified investigator (as identified on Delegation of Authority Log). Signature confirms accuracy and completeness of the SAE data as well as the investigator causality assessment including the explanation for the causality assessment.

If the SAE is associated with emergency unblinding as outlined in [Section 4.4.4 Breaking the Study Vaccine Assignment Code for Emergency], this is to be recorded on the SAE

02 Dec 2019 Astellas Page 62 of 111

worksheet. Within the SAE worksheet, the investigator is to include when unblinding took place in association with the SAE.

For contact details, see [Section II Contact Details of Key Sponsor's Personnel]. Fax or email the SAE/Special Situations Worksheet to:

Astellas Pharma Global Development – United States
Pharmacovigilance
[contact]
Email: [contact]

The following minimum information is required:

- International Study Number/Study number,
- Subject number, sex and age,
- The date of report,
- A description of the SAE (event, seriousness criteria),
- Causal relationship to the study vaccine (including reason), and
- The drug provided (if any) (blinded regimen is also an option)

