7.2.2 Per Protocol Set (PPS)

The PPS will be used to assess immunologic response and will serve as a supportive analysis. The PPS will exclude the following subjects:

- Subjects who are given antibiotics within 7 days prior to the 30-day blood draw to assess immunogenicity in the ASP3772 immunization group since these may interfere with the immunogenicity assay
- Subjects who have their 30-day blood draw 14 or more days after the 30 day post immunization scheduled blood collection
- Subjects who receive immunosuppressants as this may interfere with their ability to mount a response to the vaccine
- Subjects who have newly diagnosed immunologic abnormalities within the first 2 weeks after receiving the immunization.

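### Section 5.1.3 allows withdrawal from the whole study for excluded-medication use after a single injection, which ends scheduled collection of new safety events and does not match 5.1.5 and 6.1

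*Protocol*

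**What the plan says.** **Dosing.** Each vaccinee gets one injection on Day 1. For the test vaccine, Protocol 5.1.1 states: "Subjects randomized to ASP3772 will receive a single immunization of ASP3772".

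**Excluded medication.** Protocol 5.1.3 bars other immunizations, blood products and immunosuppressants (systemic steroids among them) "from first study vaccine administration until 30 days postimmunization". If a health condition makes one of these necessary, the investigator and medical monitor "will discuss the case and determine if the subject should be withdrawn from the study", and the use is recorded as a deviation. The synopsis has the same text. Protocol 8.3 adds a general sponsor decision on whether a subject with a major deviation continues.

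**Grounds for leaving.** Protocol 5.1.5 and 6.1 each list two: loss to follow-up and the subject's own decision ("Subject voluntarily withdraws from the study at any time for any reason"). Excluded medication is not listed.

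**Safety follow-up.** For Group 2, Protocol 2.2.1 states: "Safety assessments for SAEs and MAAEs including PIMMCs and NOCDs will continue through day 180 postimmunization". Group 1 has the same horizon; Group 3 stops at Day 30. Under Protocol 5.5.5, expedited SAE reporting "will continue until 180 days after study vaccine administration in Groups 1 and 2", and to Day 30 in Group 3, "or until the subject is determined to be a screen failure or withdraws from the study".

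**Analysis.** The PPS, a supportive set, leaves out "Subjects who receive immunosuppressants as this may interfere with their ability to mount a response to the vaccine" (Protocol 7.2.2). Excluded treatment is deviation PD4 (Protocol 7.8).

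**The concern.** Withdrawing a subject from a multi-dose trial can prevent a further dose. Here no dose remains, so withdrawal under 5.1.3 changes only what is observed afterwards.

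Safety and tolerability are the primary objective in both stages, and MAAEs, PIMMCs and NOCDs are named within the primary endpoint. Starting a systemic steroid or an immunosuppressant may itself be related to an immune-mediated problem. A rule that lets such subjects leave scheduled follow-up could therefore remove observation time selectively. With 99 subjects planned per dose in Stage 2, single events carry weight.

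The grounds for leaving also differ between sections, so two sites could treat the same case differently. Protocol 7.8 makes it a deviation (PD2) to keep a subject who has developed withdrawal criteria. A site that keeps such a subject cannot tell from the text whether that is itself a deviation.

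**Working it through.** The plan states no figure on this point, so there is none to reproduce. The check is a reading of the rules side by side, then simple arithmetic on the observation window.

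**Step 1. What happens to each type of event after withdrawal under 5.1.3**

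- *The event that prompted the medication.* It comes before the withdrawal. It is recorded as an AE, and as an MAAE or PIMMC where it qualifies (5.5.1). The subject stays in the SAF, which is everyone immunized (7.2). Section 5.5.6 requires AEs to be followed to resolution or full characterization, including after discontinuation. It is captured.
- *A new SAE.* Section 5.5.5 ends SAE reporting at withdrawal. Section 5.5.6 still requires the investigator to notify the sponsor of a later event, but only one that the investigator learns of and thinks may be related.
- *A new MAAE or PIMMC.* These are collected up to the last follow-up visit (Protocol 5.4.1; SAP 6.2.1.1). Nothing schedules a contact after withdrawal. Under normal follow-up they are collected whatever their cause, so the learned-of-and-related route in 5.5.6 is narrower.
- *An NOCD.* The definition in 5.5.1 requires that the event be unresolved at the follow-up telephone call. Without that call the classification cannot be made.
- *Exit assessments.* Section 6.1 requests the Day 30 assessments at exit only from subjects who withdraw consent. A subject withdrawn by decision under 5.1.3 is not covered.

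A later event that is not collected enters the SAF summaries as no event, because the subject stays in the set and missing data are not imputed (7.10).

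**Step 2. Length of the exposed window**

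Inputs: medication restriction Day 1 to Day 30 (5.1.3); scheduled SAE, MAAE, PIMMC and NOCD collection to Day 180 in Groups 1 and 2 and to Day 30 in Group 3 (5.4.1, 5.5.5). For withdrawal on day *d*:

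- Groups 1 and 2: days lost = 180 − *d*; share lost = (180 − *d*)/180
- Group 3: days lost = 30 − *d*

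| Day of withdrawal | Groups 1 and 2: days lost | Share of 180 | Group 3: days lost |
|---|---|---|---|
| 1 | 179 | 99% | 29 |
| 7 | 173 | 96% | 23 |
| 15 | 165 | 92% | 15 |
| 30 | 150 | 83% | 0 |

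**Step 3. Number of subjects affected**

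The documents give no rate of excluded-medication use, no proportion of such users who would be withdrawn, and no background rate of PIMMC or NOCD. The window per subject is known; the number of missed events is not.

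**Step 4. Does the immunogenicity analysis need the withdrawal?**

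Use is already recorded as PD4, and immunosuppressant users already leave the PPS. The PPS rule does not name blood products or other vaccines, and the primary immunogenicity analyses use the FAS, so the handling is partial. Withdrawal is still not what protects the analysis: it would not remove an already measured subject from the FAS.

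**The case against.** The strongest reply is that little is lost. Several parts of it stand.

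- **A reader might infer that the reaction treated with a steroid disappears from the safety counts.** The documents do not support this: that event is recorded before withdrawal, stays in the SAF and is followed afterwards under 5.5.6. No downward bias on it can be claimed.
- **A reader might infer that all SAE, MAAE and PIMMC collection ends.** That is also too strong. Only scheduled collection of new events lapses; the notification duty in 5.5.6 remains. The cut-off in 5.5.5 is written for SAE reporting, and whether it covers a subject withdrawn by others' decision is not clear. The text for MAAEs and PIMMCs has no explicit cut-off, but it depends on visits that a withdrawn subject is not scheduled to have.
- **Withdrawal is discretionary**, and the trigger is confined to the first 30 days. This stands.
- **The two-item lists in 5.1.5 and 6.1 are not worded as exhaustive**, and 7.3.1 expects AE and protocol deviation among discontinuation reasons. This makes the conflict a mismatch to reconcile, not a strict contradiction.
- **The 180-day window overstates the effect on some tables.** TEAEs stop at Day 30, and SAP 7.5.1 tabulates MAAEs, PIMMCs and NOCDs as TEAEs. For tables built that way the loss is 30 − *d* days, at most 29. Collection to Day 180 is still planned and would be cut short.
- **Acute signals are protected separately.** Section 5.1.5 pauses dosing for DEC review after, for example, a vaccine-related SAE.
- **A reader might infer that these are the subjects most at risk of an immune-mediated event, and that the loss would fall mainly on ASP3772.** The documents give no rates. Stage 2 admits subjects with stable chronic disease, who may need such medication for unrelated reasons; investigators are blinded; and the link is weaker for blood products.

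**Conclusion.** The point holds in a limited form. After a single dose, 5.1.3 and the synopsis permit a withdrawal that withholds no study treatment and ends scheduled collection of new SAEs, MAAEs, PIMMCs and NOCDs. Events at risk are those after withdrawal that the site does not learn of or does not think related, and NOCD status that depends on the follow-up call. The exposed window is 150 to 179 of 180 days per withdrawn subject in Groups 1 and 2, and up to about 30 days in Group 3. This rests on reading withdrawal in 5.1.3 as the withdrawal that ends reporting in 5.5.5, which the text suggests but does not state.

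The number of subjects affected, the number of events missed, and the size or direction of any difference between arms cannot be estimated from the documents. The case for change is that the rule would lose primary-endpoint data if followed, gains little for the analysis, and is not aligned with 5.1.5 and 6.1.

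**What to change.** 1. Reconcile 5.1.3, the synopsis and the continuation wording in 8.3 with 5.1.5 and 6.1, so that the grounds for leaving the study are the same throughout.
2. State in 5.1.3 that excluded-medication use is recorded as PD4 and leads to PPS exclusion where 7.2.2 applies, and that the subject stays in scheduled safety follow-up (Day 180 in Groups 1 and 2, Day 30 in Group 3) unless consent is withdrawn.
3. Reconcile 5.5.5 with 5.5.6, so that it is clear what is collected, and how, once a subject has left the study.

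The cost is protocol wording. The visits and the Day 180 contact, which may be a telephone call, are already scheduled. No dose, vaccination schedule or medical care changes.

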Visit Days (Window)	-28 to -3	1	7 (+1)	30 (±2)*	180 (±14)§
Informed Consent ^b	X				
Inclusion/Exclusion Criteria	X	X†			
Randomization ^c		X†			
Demographics	X				
Medical History ^d	X	Χţ			
Physical Examination ^e	X	X†		X	
Routine 12-lead ECG	X	Χţ	X	X	
Virology ^f	X				
Urine Drug Screen ^g	X	X†			
Pregnancy Test ^h	X	X†		X	
Height, Body Weight	X				
Study Immunization		X			
Vital Signs (blood pressure, pulse rate, body temperature) ⁱ	X	X†	X	X	
Clinical Laboratory Tests (hematology biochemistry, coagulation profile, hepatic profile, urinalysis) ^j	X	X†‡	X	X	
Serum sample for Immunogenicity		Χţ		X	
Serum sample for Anti-biotin Antibodies		X†		X	X^{l}
Whole-blood sample for T-cell Immune Response Measurement		Χţ	X	X	
Prior/Concomitant Medication ⁿ				\rightarrow	
Reactogenicity ^o		<	\longrightarrow		
AEsp					
SAEs ^p	<				
MAAEs including PIMMCs and NOCDs ^p		<			\longrightarrow

AE: adverse event; ECG: electrocardiogram; MAAE: medically attended adverse event; NOCD: new-onset chronic disease; PIMMC: potential immune-mediated medical conditions; SAE: serious adverse event; WBC: white blood cell.

Footnotes continued on next page

02 Dec 2019

Astellas

Page 29 of 111

- CONFIDENTIAL -
- † To be performed prior to administration of study vaccine. **Note:** Vital signs will also be performed after the administration of the study vaccine.
- \ddagger Not required if collected at a screening visit, which is ≤ 7 days from dosing visit.
- § Visit conducted as a phone call unless anti-biotin antibodies were elevated at day 30 visit.
- * If a subject has received any systemically absorbed antibiotics between day 1 and day 30, the visit should take place at least 7 days after the last dose of the antibiotics.
- a. Screening will be completed up to 28 days prior to study immunization. Subjects will be assigned a subject number for use throughout the study at the screening visit via the Interactive Response Technology (IRT) system
- b. Informed consent must be obtained prior to the performance of any study-related procedure and before Randomization.
- c. Subjects will be randomized via the IRT at the dosing visit.
- d. Medical history will be collected at screening in order to assess Inclusion/Exclusion criteria and will be reconfirmed prior to study immunization.
- e. A physical examination will be performed at the screening visit (days -28 thru -3), prior to study immunization (day 1) and day 30 visits.

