- § Visit conducted as a phone call unless anti-biotin antibodies were elevated at day 30 visit.
- * If a subject has received any systemically absorbed antibiotics between day 1 and day 30, the visit should take place at least 7 days after the last dose of the antibiotics.
- a. Screening will be completed up to 40 days prior to study immunization. Subjects will be assigned a subject number for use throughout the study at the screening visit via the Interactive Response Technology (IRT) system.
- b. Informed consent must be obtained prior to the performance of any study-related procedure and before randomization.
- c. Subjects will be randomized via the IRT system at the dosing visit.
- d. Medical history will be collected at screening in order to assess Inclusion/Exclusion criteria and will be reconfirmed prior to study immunization.
- e. A physical examination will be performed at the screening visit (days -40 thru -3), prior to study immunization (day 1) and day 30 visits.
- f. Perform tests for Hepatitis B surface antigen (HBsAg), hepatitis A virus antibodies (immunoglobulin M), HCV antibody (anti-HCV) confirmed by reflex testing (HCV-RNA) and HIV antigen/antibody (type 1 and/or type 2) at screening.
- g. Body temperature, blood pressure and pulse rate will be assessed in a sitting position. At the dosing visit, body temperature, blood pressure, pulse rate and respiratory rate will assessed predose at approximately 30 min and 1 hour postdose. Predose vitals should be collected close to the immunization and should not be more than 30 minutes prior to the dose administration. Body temperature will be collected by the subject daily through day 7 following the study immunization.
- h. Perform test for hematology (hemoglobin, hematocrit, erythrocytes, leukocytes, differential WBC, platelets), biochemistry (sodium, potassium, calcium, chloride, glucose, total cholesterol, triglycerides, blood urea nitrogen, creatinine, total protein, albumin, c-reactive protein), coagulation profile (prothrombin time, activated partial thromboplastin time, fibringen), hepatic profile (alkaline phosphatase, aspartate transaminase, alanine transaminase, y-glutamyltransferase, total bilirubin, lactate dehydrogenase), urinalysis (using dipstick - protein, glucose, pH, blood, leukocytes, urobilinogen, bilirubin, ketones, nitrite, urine microscopy [optional]).

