12.4 List of Excluded Concomitant Medications

Subjects must not use any of the following:

- Vaccines, blood product, immunosuppressants including systemic steroids (topical steroids will be allowed) from the day of study administration until 30 days postimmunization.
- Subjects may receive other routine immunizations at the 30-day follow-up visit after the completion of all study procedures at each site's discretion; however routine vaccines should not be given in less than 30 days post-study immunization.
- Acetaminophen and NSAIDs are allowed during the study, but not within 24 hours prior to immunization and collection of serum samples for immunogenicity.
- Use of any systemically absorbed antibiotics during the 30-day period prior to collection of the immunogenicity samples should be restricted unless clinically warranted (e.g., avoid prophylaxis) to avoid interference with the immunoassay. If a subject has been treated with any systemically absorbed antibiotics between day 1 and day 30, the 30-day follow-up visit should take place at least 7 days after the last dose of the antibiotics.

02 Dec 2019 Astellas Page 86 of 111

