- n. All observed or spontaneously reported AEs, inclusive of MAAEs, PIMMCs and NOCDs will be documented. AEs will be assessed at the study immunization visit, before and approximately 60 minutes after immunization. MAAEs will be reported through day 180. The investigator will avoid leading questions to influence reporting of AEs.

Table 3 Schedule of Assessments - Stage 2: Subjects 65 to 85 Years of Age and Received PCV13 Within a Year of Randomization (Group 3)

Assessments	Visit Number	Screening ^a	Dosing	Follow-up
	Visit Day (Window)	1 -40 to -3	2 1	3 30 (±2)
Informed Consent ^b		X		
Inclusion/Exclusion Criteria		X	X†	
Vaccine assignment ^c			X†	
Demographics		X		
Medical History ^d		X	X†	
Physical Examination ^e		X	X†	X
Routine 12-lead ECG		X	X†	X
Virology ^f		X		
Height, Body Weight		X		
Study Immunization			X	
Vital Signs (blood pressure, pulse rate, body temperature) ^g		X	X†	X
Clinical Laboratory Tests (hematology, biochemistry, coagulation profile, hepatic profile, urinalysis) ^h		X	X†‡	X
CCI				
Serum sample for Immunogenicity			X†	X
Prior/Concomitant Medication ^j		↔	↔	→
AEs ^k		↔	↔	→
SAEs ^k		↔	↔	→
MAAEs including PIMMCs and NOCDs ^k		↔	↔	→

AE: adverse event; ECG: electrocardiogram; MAAE: medically attended adverse event; NOCD: new-onset chronic disease; PCV13: Prevnar 13; CCI: ; PIMMC: potential immune-mediated medical conditions; SAE: serious adverse event; WBC: white blood cell.

† To be performed prior to administration of study vaccine. **Note:** Vital signs will also be performed after the administration of the study vaccine.

‡ Not required if collected at a screening visit, which is ≤ 7days from dosing visit.

Footnotes continued on next page

- a. Screening will be completed up to 40 days prior to study immunization. Subjects will be assigned a subject number for use throughout the study at the screening visit via the Interactive Response Technology (IRT) system.
- b. Informed consent must be obtained prior to the performance of any study-related procedure and before assigning vaccine via the IRT system.
- c. Subjects will be assigned a vaccine via the IRT system at the dosing visit.
- d. Medical history will be collected at screening in order to assess Inclusion/Exclusion criteria and will be reconfirmed prior to study immunization.
- e. A physical examination will be performed at screening visit, prior to study immunization (day 1) and day 30 visits.

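### The Group 3 schedule omits the antibiotic deferral of the Day 30 draw that the protocol text applies to every subject, and the analysis sets do not reliably catch an early draw

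*Protocol*

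**What the plan says.** **Body text.** Protocol 5.1.3 sets the trigger without naming a group: "If a subject has been treated with any systemically absorbed antibiotics between day 1 and day 30". It then requires that "the day 30 follow-up visit should take place at least 7 days after the last dose of the antibiotics". The purpose of restricting antibiotics before sampling is given as "to avoid interference with the immunoassay". The synopsis (concomitant medication restrictions) has the same rule, and Appendix 12.4 repeats it: "the 30-day follow-up visit should take place at least 7 days after the last dose of the antibiotics". None of the three exempts Group 3.

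**Schedules.** Tables 1 and 2 mark the Day 30 column with an asterisk. The footnote opens with "If a subject has received any systemically absorbed antibiotics between day 1 and day 30, the visit should take place at least 7 days after", counted from the end of antibiotic dosing. Table 3 shows day 30 (±2) with no asterisk, and its notes do not mention antibiotics. The SAP copies of the three tables show the same pattern.

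**Analysis sets.** The FAS, which is primary for immunogenicity, takes every immunized subject with a post-immunization measurement, whatever antibiotics were given. The PPS is supportive. Protocol 7.2.2 and SAP 5.2 remove subjects given antibiotics in the 7 days before the draw, "since these may interfere with the immunogenicity assay", but limit this to ASP3772 recipients. SAP 7.2.1 describes the same criterion with no limit by vaccine, and treats the PPS as something produced only if needed.

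**The concern.** A Group 3 site that schedules from Table 3 sees a fixed window and no instruction to wait. A site that follows 5.1.3 must sometimes break that window. Group 3 practice may therefore differ between sites, and from practice in Groups 1 and 2, on a matter that the protocol itself links to assay interference.

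Group 3 is the only source of the PPSV23 response, and a Stage 2 secondary objective sets ASP3772 against that response for the serotypes outside PCV13. An affected Day 30 value would enter the Group 3 GMT or GMC, the fold rise and the 4-fold rate. Exclusion criterion 18 bars antibiotics in the week before day 1, so the baseline value would not carry an offsetting error.

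**Working it through.** The plan gives no figure to reproduce. The check is a day count, a comparison of the set definitions, and an illustration of scale.

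**1. Can both instructions be met?** The Table 3 window is day 28 to 32. The earliest draw allowed by 5.1.3 is the day of the last dose + 7.

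- Draws on day 28, 30 and 32 leave a 7-day gap only if the last dose was on or before day 21 (28 − 7), 23 (30 − 7) and 25 (32 − 7).
- Last dose on days 22 to 25: the earliest draw is day 29 to 32. Both can be met, but an earlier draw that Table 3 permits would break 5.1.3.
- Last dose on days 26 to 30: the earliest draw is day 33 to 37. Both cannot be met.

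**2. Does an analysis set remove an early Group 3 draw?**

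| Set | Where defined | Removes it? |
|---|---|---|
| FAS | Protocol 7.2, SAP 5.1 | No |
| PPS | Protocol 7.2.2, SAP 5.2 | No, ASP3772 recipients only |
| PPS | SAP 7.2.1 | Yes, as worded |

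The two SAP descriptions of the PPS disagree, so the answer depends on which one is programmed. Under the narrower wording, PCV13 recipients are not covered either.

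**3. Would a deferred draw be lost?** No. Days 33 to 37 lie inside the SAP 7.7.3 Day 30 window (D16 to D46). They also lie before day 44 (30 + 14), when the PPS lateness exclusion begins.

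**4. Scale, under assumptions.** The documents give no rate of antibiotic use, no size or direction of interference, and no GSD. Suppose that m of 99 Group 3 values are each multiplied by k. The geometric mean is then multiplied by k^(m/99):

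| m | k = 0.25 | k = 10 |
|---|---|---|
| 1 | 0.986 | 1.024 |
| 5 | 0.932 | 1.123 |
| 10 | 0.869 | 1.262 |

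With unaffected baselines, the GMFR moves by the same factor. A 4-fold rate can move by at most m/99, for example 5/99 = 5.1 percentage points.

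For comparison, the 95% confidence limits in SAP Appendix A lie a factor GSD^(t/√n) either side of the mean. At n = 99 this is 1.245, 1.379 and 1.514 for assumed GSDs of 3, 5 and 8. With up to 5 affected subjects, every shift in the table is smaller than that factor. Only 10 affected subjects at k = 10 (1.262) reach the smallest of the three.

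**The case against.** The strongest reply is that nothing is missing. The deferral is stated in the synopsis, 5.1.3 and Appendix 12.4, and all three bind Group 3 sites, so a silent table does not cancel it. This largely stands. The defect is an inconsistency between schedule and text, and a reader who concluded that Group 3 has no deferral rule would be wrong. It remains that the schedule sites work from gives a window that the text sometimes forbids.

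A second reply is that the other arms are not clean either. The rule says only that the visit should be deferred, in every group, and the FAS keeps undeferred ASP3772 and PCV13 draws. This stands: the documents do not support an inference that the ASP3772 arms are free of affected samples.

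A third is that the comparison is loose. Group 3 is non-randomized and previously vaccinated with PCV13, and it is summarized separately. SAP 7.1 compares post-dose with pre-dose for the serotypes unique to ASP3772. No test against PPSV23 appears in the visible text. This also stands and limits what is at stake, but the reference still serves a stated secondary objective.

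**Conclusion.** The inconsistency is confirmed and minor. Schedule and text conflict outright for a last dose on days 26 to 30 and leave room for an early draw for days 22 to 25. Whether any analysis removes such a draw depends on two conflicting definitions of the PPS. Group 3 summaries can therefore include antibiotic-affected samples.

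A reader might go further and infer that residual antibiotic raises the OPA titre, inflates the PPSV23 reference and makes ASP3772 look worse. The documents do not support this. They say only that antibiotics may interfere with the assay, give no direction or size, and do not single out OPA. Direction and size therefore cannot be derived. The view that any effect is probably small rests on assumptions: few of the 99 subjects affected, k between 0.25 and 10, and a GSD of 3 to 8. No formal test and no sample size is affected.

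**What to change.** - Reconcile Table 3 in the protocol and the SAP with the synopsis, 5.1.3 and Appendix 12.4, so that schedule and text state one timing rule for the Group 3 draw. Which rule governs is for the sponsor to decide.
- Word the PPS antibiotic criterion identically for all vaccine groups in protocol 7.2.2, SAP 5.2 and SAP 7.2.1.
- Add a sensitivity summary of Group 3 OPA and IgG (GMT or GMC, GMFR and 4-fold rates) without samples drawn within 7 days of antibiotics.

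**Cost.** Text edits in both documents and one extra summary. No new data are needed, because Group 3 concomitant medications are already collected through the Day 30 visit. If the deferral is kept for Group 3, a few draws will fall outside ±2 days. For a last dose by day 30, a draw made once the 7 days have passed (days 33 to 37) stays usable under the SAP Day 30 window and the PPS lateness limit.
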